8.1 Collection and Storage of Data

REDCap data management software will be used to organize all data including documentation of informed consent, self-report measures, and clinical data. REDCap is supported at UI by NIH CTSA awards. All study information including PHI will be collected in a secure RedCap interface housed at the UI. Self-report measures will be collected after study enrollment. Subjects will be provided with a computer link and instructions for completion of surveys from home during the

week prior to the beginning of the group. Clinical data will be extracted from the medical record by study team members. Intervention website usage will be extracted from the administrator page by study team members.

There may be situations in which subjects would prefer to complete surveys using hard copies. In this situation, hard copy data will be hand entered into RedCap by study team members. When entering subject data, research assistants are only aware of the individual's subject number for the study. All materials are labeled with subject ID and not labeled with any other identifying information (medical record number or name). RedCap data identified only by subject ID may be downloaded into SPSS files kept on password protected servers in the Department of Psychological and Brain Sciences. These password protected files are only available to team members who have set up access through Information Technology Systems ([name]). Electronic data is stored only on these servers. The exception is that data which is being statistically analyzed by the PI or project statisticians is on password protected computers.

8.2. Screening Log

Information collected will include an individual's address, phone number and e-mail address, subject number and reason for not enrolling e.g., exclusion, lack of interest, currently excluded but may be eligible in the future. Women who are screened that do not enroll may subsequently be able to participate. For example, this would apply to individuals currently finishing chemotherapy who will be eligible when they complete it or to survivors whose availability does not fit the timing of the current group but will fit the timing of the next group being offered. The screening log will be kept so that these individuals can be called back when they either become eligible or a group is being offered that would work for them.

8.3. How Long Are Records Kept

For survivors who are eligible and approached but decline participation, their identifiers will be kept until the end of enrollment and then destroyed to make sure we do not contact them again. Similarly, for survivors who are ineligible, their identifiers will be kept until the end of enrollment to avoid their being evaluated again. They will be destroyed at 3 years post-chemotherapy or the end of the study whichever comes first. Information of subjects that are temporarily ineligible but may become eligible following the end of treatment or involvement in another study will be kept until the end of enrollment. Study records will be kept for 10 years after the close of the study to allow for complete data analysis of primary endpoints as well as moderators, mediators, and other information. Enrolled subjects who have indicated that we may contact them for future research studies will have their contact information kept for 10 years following the study.

For any study in which lowa is the lead site, the Holden Comprehensive Cancer Center's (HCCC) Data Safety Monitoring Committee(DSMC) will be the DSMB of record. If the participating sites will be performing any onsite monitoring or auditing activities during the course of the study, any resulting reports should be sent to HCCC's DSMC. It will have oversight of overall data and safety monitoring for all sites. The level of DSMC monitoring and oversight is dependent on the risk level assigned to the protocol at the time of initial PRMC/DSMC review. Basic requirements entail subject registration in OnCore, documentation of adverse events and protocol deviations, and annual review by the DSMC. Regardless of risk level, all studies are required to have data collection forms developed in OnCore (eCRFs) to facilitate data and safety review by the DSMC. The Holden Comprehensive Cancer Center has a protocol development coordinator who is available to assist investigators with their protocol documents. This person serves as a point of contact between PIs, regulatory, and clinical staff to ensure the document includes all the necessary components prior to committee review. There also is an eCRF developer who works

with investigators and staff to ensure data collection forms meet all the necessary requirements. The complete Data and Safety Monitoring Plan is attached.

9. References

10.1 DATA AND SAFETY MONITORING PLAN

Type of Clinical Trial:

☑ Investigator-initiated (UI/F		Investigator-initiated, participating site
Pilot study		Phase I
Phase I/II		Phase II
Phase III		Compassionate-use/Expanded Access
Interventional Treatment	\checkmark	Interventional Non-Treatment
Non-Interventional		

Study risk-level:

- \Box Level 1—low risk of morbidity or death, * <1% of death or any adverse event
- \checkmark Level 2—risk of death* <1% or any adverse event 1% 5%
- \Box Level 3—risk of death* 1% 5% or grade 4 5 SAE 1% 5%
- \Box Level 4—risk of death* >5% or grade 4 5 SAE >5%
- Drugs being used on a "compassionate" basis
- * Risk of death" refers specifically to 100-day treatment-related mortality

Reporting and Monitoring Requirements:

All institutional investigator initiated trials (IITs), regardless of assigned risk level are subject to routine DSMC monitoring activities which may include but are not limited to review of signed consent documents, eligibility and adverse event reporting.

All institutional IITs have the following **reporting requirements** as part of their DSMP:

- Register all subjects in HCCC's Clinical Trial Management System, OnCore
- Document Adverse Events
- Document protocol deviations
- Provide an annual progress report to the DSMC via OnCore data export

Selected monitoring strategy based on risk-level:

Risk Level 2

Interventional trials with a risk of death^{*} (<1% or any adverse event 1% - 5%), e.g. behavioral interventions, nutritional therapies, low risk procedures (e.g., endoscopy, glucose-tolerance tests, induced sputum, skin or muscle biopsy, nasal wash, lumbar puncture, bone marrow biopsy,

imaging requiring sedation), as well as therapeutic trials involving agents with known safety profiles already licensed for the indication and age group. Most disease-prevention trials will be considered at least a Risk Level 2.

Study Safety Review

The PI or designated study personnel will review all study data for completeness.

Additional Reporting Requirements

 Serious adverse events will be entered directly into an OnCore SAE report by the research team. OnCore will send an automatic notification to the DSMC Chair/acting Chair and staff for review.

Routine Adverse Event Reporting

For non-serious Adverse Events, documentation must begin from the first day of study intervention and continue through the 30 day follow-up period after the study intervention is discontinued.

Collected information should be recorded in the electronic/Case Report Forms (eCRF/CRF) for that subject. A description of the event, its severity or toxicity grade (according to NCI's Common Toxicity Criteria (CTCAE 5.0)), onset and resolved dates (if applicable), and the relationship to the study drug should be included. Documentation should occur in real time. The principal investigator has final responsibility for determining the attribution of the event as it is related to the study drug.

Serious Adverse Event Reporting

For any experience or condition that meets the definition of a serious adverse event (SAE), recording of the event must begin after signing of the informed consent and continue through the 30 day follow-up period after treatment is discontinued.

Investigators must report to the DSMC any serious adverse events (SAE), whether or not they are considered related to the investigational agent(s)/intervention (21 CFR 312.64). SAEs must be reported via an OnCore SAE Report within 24 hours of learning of the event. An adverse event is considered **serious** if it results in ANY of the following outcomes:

- An adverse event is considered **serious** in it results in Aive of the following
 - 1. Death
 - 2. A life-threatening adverse event
 - 3. An adverse event that results in inpatient hospitalization OR prolongation of existing hospitalization for ≥ 24 hours
 - 4. A persistent or significant incapacity or substantial disruption of the ability to conduct normal life functions
 - 5. A congenital anomaly/birth defect.
 - 6. Important Medical Events (IME) that may not result in death, be life threatening, or require hospitalization may be considered serious when, based upon medical judgment, they may jeopardize the patient or subject and may require medical or surgical intervention to

prevent one of the outcomes listed in this definition. (FDA, 21 CFR 312.32; ICH E2A and ICH E6).

Data Monitoring and Management

Subject Registration

All studies that undergo PRMC review and/or utilize HCCC Clinical Research Services (CRS) resources are required to register subjects in OnCore. Each subject registration includes the following:

- The subject's IRB approved (version date) consent form and the date of their consent.
- Date of eligibility and eligibility status (eligible, not eligible)
- On study date and subject's disease site (and histology if applicable)
- On treatment date (if applicable)

All subject registration information is expected to be entered into OnCore within 2 (two) business days after the subject's study visit.

Subject Data

For HCCC investigator initiated trials, research staff are responsible for entering subject study data (data collection) into OnCore electronic case report forms (eCRFs). These eCRFs must be approved by the PI and statistician prior to study activation to ensure sufficient and necessary data acquisition. All information entered into eCRFs will be traceable to the source documents which are generally maintained in the subject's file.

eCRF data entry needs to be timely and should be entered into OnCore as soon as possible but no later than **14 (fourteen) business days** after the subject's visit, including adverse events, tumor measurements, administration of study medication, concomitant medications, labs, and vitals. Physical exam assessments must be entered no later than **14 (fourteen) business days** following completion of the physician's clinic note in the medical record.

Timely data entry facilitates remote monitoring of data, allows the data to progress appropriately through the data cleaning process, and helps prevent a backlog of data queries.

Forms Monitoring

OnCore eCRF data are monitored on a routine basis (dependent on accrual) to ensure all data are entered completely, accurately, and within time requirements outlined above. The assigned DSMC monitor will coordinate and complete the data monitoring review. When the time comes to monitor a study (based on patient accrual and assigned risk level of trial) the monitor arranges for a selection of cases to be reviewed from among the subjects registered in OnCore. As part of the forms monitoring process, the assigned monitor will issue queries via OnCore (linked to the eCRF) to resolve missing, incomplete, and/or incorrect information. A member of the research team is expected to respond to these monitoring queries within **14 (fourteen) business days**.

The monitoring process can often identify misunderstandings or deficiencies in the written, research protocol requirements earlier in the study process and thereby improve data quality and reduce rework.

Final Reports

A summary of each subject's data record is continually available to the PI, research staff, and DSMC from OnCore's Biostat Console. The availability of this information is a valuable tool for the preparation of final reports and manuscripts as well as ongoing deficiency reports.

Antoni, M. H., et al. (2006). "How stress management improves quality of life after treatment for breast cancer." J Consult Clin Psychol 74: 1143-1152.

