Blood spots will be collected before randomization of the intervention and again within 2 weeks following the end of the 11-week intervention. If subjects consent to this sub-study, they will be provided with two small kits that will contain a lancet to do the finger-prick, an alcohol swab for sterilizing their skin, cotton gauze for cleanup, a band aid, the blood spot collection card, and a pre-paid return envelope for sending the materials back. After subjects who have consented for the substudy receive their bloodspot kits, they can be contacted over the phone and walked through the process if necessary. They will be provided with reference materials on how to use items in the bloodspot kit. Subjects will then return the completed Blood Spot Card in the pre-paid envelope. They will also be contacted at the end of the group intervention and walked through the process a second time should this be considered necessary for their post group finger prick.

TABLE 3. FLOW CHART OF STUDY TIME-POINTS

Procedures	Screening	Enrollment	Pre-Randomization	Randomization ^d	Pre-Group Activities	Week 1	Week 2	Week 3	Week 4	Week 5	Week 6	Week 7	Week 8	Week 9	Week 10	Week 11	Week 12	Week 19-20	Week 26	Week 39-40	Week 52	
Screening	Х																					
Informed consent		Х																				
Demographics		Х																				
Medical history ^a	Х	Х																				
Assessments ^b			Х														Х		Х		Х	
Randomization ^c				Х																		
Technical training			Х		Х																	
Group introduction						Х																
Study intervention							Х	Х	Х	Х	Х	Х	Х	Х	Х	Х						
Booster sessions																		Х		Х		
Adverse event review						x	x	x	x	x	x	x	x	x	x	x	x	x	x	x	x	
& evaluation						^	^	^	^	^	^	^	^	^	^	^	^	^	^	^	^	
a: Disease and treatment status b: FACT-O, PSS, AAQ-II, BEAQ, FACIT-F, MOCS, CESD, POMS-SF, FMI, CWS, Brief COPE, SPS, PSQI, Godin, PHQ, demographics, COVID survey c: See section 6.0 for randomization process d. technical training and pre-group assessments may occur before or after randomization																						

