6.5. Risks

Based on our previous work, this study as described is of minimal risk. Minimal risk is defined as the probability and magnitude of harm or discomfort anticipated in the research not greater than that ordinarily encountered in daily life or during routine physical or psychological exam.

During the psychosocial questionnaire administration, there are minimal potential emotional risks to subjects due to the somewhat personal nature of the questions asked regarding mood and quality of life. Answering the questions may make subjects upset or uncomfortable; subjects will be informed that they can choose not to answer questions they do not wish to answer.

During the group conferencing sessions, sensitive topics may be discussed; subjects are free to participate as much or as little as they feel comfortable.

There is a potential loss of confidentiality from the web conferencing format; all subjects will be instructed in confidentiality practices at the beginning of the groups (see below).

Risks of Immune Response Sub-Study

Slight discomfort or stinging sensation when using the lancet. Small risk of infection and/or bruising.

What Is Done To Minimize The Risks

Because interactions will be in a group setting, in the first session subjects will be instructed about the importance of confidentiality. They will be required to access the web-based intervention in a private location where others could not overhear the group conversation. Additionally, subjects can choose to disclose as much or as little personal information as they feel comfortable with in the group. Confidentiality of subject information will be strictly preserved, and subject names will not be revealed in publications or reports.

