Subjects will be informed that they may withdraw from the study at any time, with no penalty, should this occur; conversely, we will attempt to resolve any problems causing these responses, should survivors wish to continue participating. If a participant experiences an adverse or unanticipated event during the study, research staff in contact with that participant will notify the lead investigator at each participating site or at UI if the participant is not being followed at one of the participating clinical sites. Subjects will be asked to report any new health problems that arise in connection with the study to the study coordinator at their site or to the Coordinating and Data Core at the UI if they are not from a participating clinical site. He/she will refer the survivor to their physician for serious health problems. Should a survivor disclose high levels of emotional distress (e.g. levels of depression consistent with a diagnosis of depression [CESD > 24]) during the study period, designated study personnel will contact the participant to offer appropriate resources as determined by the lead investigators. Documentation of appropriate resources offered to the survivor and of the survivor's acceptance or rejection of the resources will be made by the Coordinating and Data Core.

Study data will be collected and managed using REDCap (Research Electronic Data Capture) electronic data capture tools supported by the Biomedical Informatics group in the UI Institute for Clinical and Translational Science. REDCap (www.project-redcap.org) is a secure, web-based application with controlled access designed to support data capture for research studies, providing: 1) an intuitive interface for validated data entry; 2) audit trails for tracking data manipulation and export procedures; 3) automated export procedures for seamless downloads to common statistical packages; and 4) procedures for importing data from external sources. For multi-center studies REDCap uses Data Access Groups (DAGs) to ensure that personnel at each institution are blinded to the data from other institutions Each study team member will be granted access to REDCap through a secure login by the study PI, study manager or their proxy. REDCap supports Two-factor authentication using DUO.

Risks of Immune Marker Sub-Study:

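### Non-serious adverse event documentation and scheduled review start with the group, after the first finger-prick and baseline survey, and the participant prompt is narrower than the SAE duty

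*Combined protocol and SAP*

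**What the plan says.** Section 10.1 (Data and Safety Monitoring Plan) sets two windows. For non-serious events, "documentation must begin from the first day of study intervention" and must "continue through the 30 day follow-up period after the study intervention is discontinued". For serious events, "recording of the event must begin after signing of the informed consent", and they go to the monitoring committee "whether or not they are considered related to the investigational agent(s)/intervention". The same section leaves attribution to the principal investigator.

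Table 3 in Section 6.3 has a row headed "Adverse event review", with marks from Week 1 (the group introduction) to Week 52 and none before.

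Two study procedures come before the group. Section 6.3 has participants complete the initial assessment once a cohort is filled, and states for the sub-study: "Blood spots will be collected before randomization of the intervention". Section 6.5 lists the risks of both: possible upset from the questionnaires and, for the lancet, stinging and "Small risk of infection and/or bruising".

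On reporting, Section 6.5 says: "Subjects will be asked to report any new health problems that arise in connection with the study". It also tells staff in contact with a participant to notify the lead investigator of untoward or unexpected events, with no condition on cause, and sets up a contact procedure for high CES-D scores.

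**The concern.** The protocol names particular harms for the finger-prick and the surveys, and its rule for recording non-serious events opens after each has been done once. Those harms are mostly non-serious by nature, so the earlier start for serious events does not cover them. A team that follows Section 10.1 to the letter has no duty to record a bruise or local infection from the first home finger-prick.

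There is a second, related gap. Serious events count from consent, but no one is scheduled to ask about them until Week 1, and the participant is asked only about problems she links to the study. Unrelated hospital admissions are foreseeable here: the protocol describes a high likelihood of recurrence and lets women who recur continue while on chemotherapy. The 24-hour reporting clock in Section 10.1 runs from when the team learns of the event, so an admission that nobody mentions may never start it.

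At stake is the completeness of the safety record sent to the monitoring committee and of the harm count for the sub-study's own procedure.

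**Working it through.** The plan gives no figure to reproduce, so the check sets the timing rules side by side.

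| Step | Timing | Non-serious window (10.1) | Table 3 review | SAE window (10.1) |
|---|---|---|---|---|
| Baseline survey | Before the group | No | No | Yes |
| First finger-prick | Before randomization | No | No | Yes |
| Group introduction | Week 1 | Unclear | Yes | Yes |
| First content session | Week 2 | Yes | Yes | Yes |
| Post-intervention survey | Week 12 | Yes | Yes | Yes |
| Second finger-prick | Within 2 weeks after the 11-week program | Yes | Yes | Yes |

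1. **Review marks.** The adverse event row has 12 marks for Weeks 1 to 12 and 4 more (Weeks 19-20, 26, 39-40 and 52), 12 + 4 = 16. The five columns before Week 1 (screening, enrollment, pre-randomization, randomization, pre-group activities) have none.

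2. **Finger-pricks.** There are two per sub-study participant. The second falls at most 14 days after the program ends, inside the 30-day follow-up. The first precedes the opening of the window: 1/2 = 50% of the procedures.

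3. **Surveys.** Table 3 has four rounds: pre-randomization and Weeks 12, 26 and 52. The first precedes the opening: 1/4 = 25%. Footnote d allows pre-group assessments after randomization, but they are still before the group. A woman rescheduled to a later group more than a month after her baseline surveys repeats them (Section 6.3), again before her group starts.

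4. **Start date.** Table 3 puts the group introduction in Week 1 but begins its intervention row in Week 2, so the first intervention day is not pinned down. On either reading it comes after the first finger-prick and the baseline survey.

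5. **Consent to Week 1.** The SAE duty applies throughout this interval with no scheduled review. The interval can be long: the Randomization section speaks of a first recruit waiting 3 months or more, Section 6.3 of waits beyond 2 months, and the Screening section accepts that women may recur or start chemotherapy meanwhile.

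6. **Prompt against duty.** Section 10.1 requires serious events regardless of relation and gives attribution to the principal investigator. The Section 6.5 prompt makes the participant judge relatedness first. An unrelated admission is therefore caught only if staff contact or the Week 1 to 52 review brings it out.

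**The case against.** The strongest reply is that the routes are broader than these gaps suggest. SAE recording opens at consent, so a serious finger-prick infection is inside the window. Staff must pass on untoward events whatever the cause, and the Table 3 review carries no relatedness filter. The participant prompt itself has no Week 1 start and would cover a finger-prick or survey harm. Section 8.1 places the surveys in the week before the group, so a lingering problem could surface at the Week 1 review. Different start dates for serious and non-serious events do not contradict each other. The harms are slight, and the finger-prick belongs to an optional sub-study.

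All of this stands, and it limits the point. It does not close the gap: a harm volunteered before the group still falls outside the rule for documenting non-serious events, and an unrelated admission still depends on someone asking.

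A reader might infer more, and the documents do not support it:

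- **That all adverse event collection opens with the first session.** This is wrong for serious events.
- **That no adverse event question exists because footnote b of Table 3 lists none.** Footnote b defines the assessments row; adverse event review is a separate row. The case report forms and consent wording were not available for this check.
- **That a psychologist in one arm and a health educator in the other would bias a comparison of harms.** Both arms also have a trainee co-facilitator, use the same reporting contacts and complete the same CES-D. Nothing says that facilitators conduct the review, and Section 7 plans no between-arm adverse event comparison.

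**Conclusion.** The concern holds as a minor one. Followed exactly, the plan leaves non-serious harms of the first finger-prick and the baseline survey outside its documentation window and its scheduled review. It also leaves the period from consent to Week 1 without a scheduled check for serious events, and its participant prompt is narrower than its SAE duty.

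The size is one of two finger-pricks and one of four scheduled survey rounds. These are counts of procedures, not of lost events. The documents give no event rates or reporting rates, so the number of missed events cannot be estimated. For serious events the risk is incomplete ascertainment, not a missing requirement.

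The conclusion assumes that the case report forms and consent wording do not already ask more broadly or earlier. No efficacy endpoint, power figure or analysis is affected.

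**What to change.** Reconcile Sections 6.3 (Table 3), 6.5 and 10.1:

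- In 10.1, start non-serious documentation at the first study procedure, or at consent as for serious events.
- In Table 3, add a pre-randomization mark to the adverse event row.
- In 6.5, ask participants for any new health problem or hospital stay, and leave relatedness to the investigator.
- Add one short adverse event and hospitalization item, identical in both arms, to the existing REDCap surveys. If the baseline survey is completed before the first finger-prick, ask the item again at the contact about the kit.

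The cost is a few wording changes, one table mark and one survey item. The downside is more unrelated events to log.
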